8.4 Significance and Adjustment for Multiple Comparisons

Change from Baseline in IOP (mmHg) at Day 28 and Day 1 (on-treatment time points) in the study eye is the primary efficacy endpoint. It will be summarized by timepoint and treatment group in the ITT population primarily and in the PP population secondarily. The differences between treatments (H-1337 vs Timolol) will be calculated for each H-1337 treatment group. A timematched longitudinal model adjusting for baseline and including a random effect for subject will be used to calculate the LSmean, SE, and 2-sided 95% CI for the between treatments differences. To account for the multiple comparisons of the primary endpoints, adjustment for multiplicity will be fulfilled by using a hierarchical testing, based on a fixed-sequence procedure defined in

Table 3. First, the primary endpoint is tested for non-inferiority at all 4 time points at Day 28 (excluding +12 hours) and all 3 on-treatment time points at Day 1 (excluding +12 hours) for the first pre-defined Group comparison listed in Table 3. If the upper limit of the 2-sided 95% CI of the difference between H-1337 and Timolol is strictly lower than the value 1.5, then non-inferiority is concluded. If non-inferiority is concluded at the 7 timepoints, then testing of the second listed Group Comparison in Table 3 can take place at the 2-sided alpha level of 0.05. Otherwise, non-inferiority cannot be concluded and no further formal testing takes place. The same sequential approach is then applied to the remaining endpoints listed in Table 3.

Table 3 Pre-defined Sequence for Hierarchical Testing

Order	Group Comparison	Non-Inferiority Criteria
1	H-1337 1.0% Ophthalmic Solution b.i.d. vs	1.5 threshold at all 7 time points
	Timolol 0.5% Ophthalmic Solution b.i.d	
2	H-1337 0.6% Ophthalmic Solution b.i.d vs	1.5 threshold at all 7 time points
	Timolol 0.5% Ophthalmic Solution b.i.d	
3	H-1337 1.0% Ophthalmic Solution q.a.m. vs	1.5 threshold at all 7 time points
	Timolol 0.5% Ophthalmic Solution b.i.d	
4	H-1337 1.0% Ophthalmic Solution b.i.d. vs	1.0 threshold at 5 or more time points
	Timolol 0.5% Ophthalmic Solution b.i.d	
5	H-1337 0.6% Ophthalmic Solution b.i.d vs	1.0 threshold at 5 or more time points
	Timolol 0.5% Ophthalmic Solution b.i.d	
6	H-1337 1.0% Ophthalmic Solution q.a.m. vs	1.0 threshold at 5 or more time points
	Timolol 0.5% Ophthalmic Solution b.i.d	

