4.7	MEDICAL AND OCULAR HISTORY	
4.8	PRIOR AND CONCOMITANT MEDICATIONS	
4.9	CONCOMITANT PROCEDURES	
4.10	Treatment Exposure	
4.11	EFFICACY ANALYSES	
4.11		
4.11		
4.11		3
4.12	SAFETY ANALYSES	_
4.12		
4.12		
4.12		
4.12	1 1 2	
4.12	J = JI = G	
4.12 4.13	7.6 Dilated Ophthalmoscopy	4
4.13 4.14	SUBGROUP ANALYSIS	
	IARY OF CHANGES FROM THE PROTOCOL16	
	OF PROGRAMMING SUMMARY & ANALYSIS TABLES17	
7 APPEN	NDICES18	
7.1	APPENDIX 1 – TIME AND EVENT SCHEDULE	

Summary of Changes

Version 1.0	Initial Version
Version 2.0	Updates to reflect Protocol Version 3.0 and comments received from U.S. FDA on 4 January 2024. The Intent-to-Treat population is redefined as per FDA's comments. The main analyses are conducted on the Intent-to-Treat population instead of the Per-Protocol population. The repeated measures model of the main analysis contains additional information as per FDA's feedback. The random effect is updated to subject instead of center. Details on diurnal intraocular pressure calculations are added.

30-Jan-24

Abbreviations

AE	Adverse Event
ANCOVA	Analysis of Covariance
ATC	Anatomical Therapeutic Chemical
BCVA	Best Corrected Distance Visual Acuity
b.i.d.	twice a day
CI	Confidence Interval
IOP	Intraocular Pressure
IP	Investigational Product
ITT	Intent-to-Treat
LS	Least Square
MedDRA	Medical Dictionary for Regulatory Activities
mmHg	Millimetre of mercury
OD	right eye
OHT	Ocular Hypertension
OS	left eye
OU	both eyes
POAG	Primary Open Angle Glaucoma
PP	Per-Protocol
PT	Preferred Term
q.a.m.	every morning
q.p.m.	every afternoon/evening
RGC	retinal ganglion cells
SAP	Statistical Analysis Plan
SD	Standard Deviation
SE	Standard Error
SOC	System Organ Class
TEAE	Treatment Emergent Adverse Event
WHODRUG	World Health Organization Drug Dictionary

1 Introduction

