4.3 Adjustment for Multiplicity

To account for the multiple comparisons of the primary endpoints, adjustment for multiplicity will be fulfilled by using a hierarchical testing, based on a fixed-sequence procedure defined in Table 1.

First, the primary endpoint is tested for non-inferiority at all 5 time points at Day 28 and all 4 ontreatment time points at Day 1 for the first pre-defined Group comparison listed in Table 1. If the upper limit of the 2-sided 95% CI of the difference between H-1337 and Timolol is strictly lower than the value 1.5, then non-inferiority is concluded. If non-inferiority is concluded at the 9 timepoints, then testing of the second listed Group Comparison in Table 1 can take place at the 2-sided alpha level of 0.05. Otherwise, non-inferiority cannot be concluded and no further formal testing takes place.

The same sequential approach is then applied to the remaining endpoints listed in Table 1. Endpoints are tested in the order defined in Table 1.

For the first 3 rows in Table 1, non-inferiority at the 1.5 threshold at all 9 timepoints must be shown to allow to proceed to the next row. For the last 3 rows in Table 1, non-inferiority at the 1.0 threshold at 5 or more timepoints must be shown to allow to proceed to the next row.

Table 1 Pre-defined Sequence for Hierarchical Testing

Order	Group Comparison	Non-Inferiority Criteria
1	H-1337 1.0% Ophthalmic Solution b.i.d. vs	1.5 threshold at all 9 time points
	Timolol 0.5% Ophthalmic Solution b.i.d	
2	H-1337 0.6% Ophthalmic Solution b.i.d vs	1.5 threshold at all 9 time points
	Timolol 0.5% Ophthalmic Solution b.i.d	
3	H-1337 1.0% Ophthalmic Solution q.a.m. vs	1.5 threshold at all 9 time points
	Timolol 0.5% Ophthalmic Solution b.i.d	
4	H-1337 1.0% Ophthalmic Solution b.i.d. vs	1.0 threshold at 5 or more time points
	Timolol 0.5% Ophthalmic Solution b.i.d	
5	H-1337 0.6% Ophthalmic Solution b.i.d vs	1.0 threshold at 5 or more time points
	Timolol 0.5% Ophthalmic Solution b.i.d	
6	H-1337 1.0% Ophthalmic Solution q.a.m. vs	1.0 threshold at 5 or more time points
	Timolol 0.5% Ophthalmic Solution b.i.d	

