4.11.1 Primary Efficacy Analyses

Change from Baseline in IOP (mmHg) at Day 28 and Day 1 (on-treatment time points) in the study eye is the primary efficacy endpoint. It will be summarized by timepoint and treatment group in the ITT population primarily and in the PP population secondarily. The endpoints will be analysed using an analysis of covariance (ANCOVA) model including baseline value and treatment groups as independent variables. The least square (LS) means, standard error (SE) and 2-sided 95% CI will be reported for each treatment group at each post-randomization visit.

In addition, the differences between treatments (H-1337 vs Timolol) will be calculated for each H-1337 treatment group. A time-matched longitudinal model adjusting for baseline and including a random effect for subject will be used to calculate the LS mean, SE, and 2-sided 95% CI for the between-treatments differences. The model will also be tested for treatment by visit and treatment by time points interactions. If no interactions are detected, the main effect model will be used. The variance-covariance matrix-structure used in the model will be the unstructured (TYPE=UN). If convergence is not achieved, a compound-symmetry structure will be used (TYPE=CS).

The testing procedure for non-inferiority will be performed as described in Section 4.3.

Missing values will not be imputed.

All summaries generated for IOP will be using the mean/median value recorded in the case report form.

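### SAP 4.11.1 does not say which part of the primary model is unstructured, and its only fallback imposes one variance on time points that are judged separately

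*SAP*

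**What the plan says.** SAP 4.11.1 takes the between-treatment differences from one model: "A time-matched longitudinal model adjusting for baseline and including a random effect for subject will be used to calculate the LS mean, SE" and the 2-sided 95% CI. On covariance it says: "The variance-covariance matrix-structure used in the model will be the unstructured (TYPE=UN" and then: "If convergence is not achieved, a compound-symmetry structure will be used (TYPE=CS". It does not say whether UN is the residual structure or the structure of the random effect. It gives no intermediate structure, no robust standard error, no degrees-of-freedom method and no definition of failed convergence. Protocol 8.4 names the random subject effect but no covariance structure.

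The SAP's change summary, used here only as context for the type of model, speaks of a repeated measures model: "The repeated measures model of the main analysis contains additional information as per FDA's feedback".

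The limits from this model decide the trial. SAP 4.3 requires that the "upper limit of the 2-sided 95% CI of the difference between H-1337 and Timolol is strictly lower than the value 1.5" at each time point, and it counts nine: "First, the primary endpoint is tested for non-inferiority at all 5 time points at Day 28 and all 4 ontreatment time points at Day 1". Protocol 8.4 leaves out +12 hours and counts seven: "If non-inferiority is concluded at the 7 timepoints, then testing of the second listed Group Comparison in Table 3 can take place". That mismatch is a separate matter; this point holds for either count.

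SAP 4.11.1 also tests treatment-by-visit and treatment-by-time interactions, and uses a main-effects model if none is detected.

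**The concern.** A fully unstructured residual matrix already contains all the covariance between a subject's readings. A random intercept adds the same constant to every element of that matrix, so data cannot separate the two. Software may report a singular or non-positive-definite matrix, or fail to converge. The SAP does not say which of these outcomes triggers the fallback, so the choice could end up being made after the fit has been seen.

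The fallback assumes the same variance for a reading two hours after the first dose and for a reading after four weeks of treatment. When a separate limit is read at each time point, a pooled variance makes it too narrow where pressure is more variable and too wide where it is less variable. The first favours a false non-inferiority conclusion at that point. The second costs power, and under rows 1 to 3 of SAP Table 1 a single failed time point ends formal testing.

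**Working it through.** **The plan's own figure.** Inputs from SAP 3.3: 45 per group, margin 2 mmHg, SD 3.0, one-sided alpha 0.05. SE = 3.0 × √(2/45) = 0.632. Power = Φ(2/0.632 − 1.645) = Φ(1.517) = 93.5% (93.2% with the t distribution). 45/0.9 = 50. The stated power of at least 90% and the 50 per group both reproduce. They do not depend on the covariance structure.

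**Is the random effect redundant?** Write the covariance of one subject's readings as V = σ_b²J + R, where J is all ones.
- Nine time points, R unstructured: 9 × 10/2 = 45 parameters, plus σ_b² makes 46. The rank is 45.
- Seven time points: 7 × 8/2 = 28, plus one makes 29. The rank is 28.
- If the random effect is kept in the fallback, random intercept plus CS has 3 parameters and rank 2.

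With residual UN, one parameter is therefore surplus. Only the split between σ_b² and R is undetermined. V itself, and with it the treatment differences and their limits, is determined.

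**What CS does to the limit at one time point.** Assume complete data, a treatment-by-time mean model and the same variances in all arms. The true SE at time t is SD_t × √(2/n). CS uses SD_pool × √(2/n), where SD_pool is the root mean square of the SD_t. The one-sided error when the true difference equals the margin is then Φ(−1.96 × SD_pool/SD_t).

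The documents give no SD by time point, so every SD_t below is an assumption. With SD_pool = 3.0:

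| SD_t | Error under CS | Nominal |
|---|---|---|
| 3.0 | 2.5% | 2.5% |
| 3.3 | Φ(−1.782) = 3.7% | 2.5% |
| 3.6 | Φ(−1.633) = 5.1% | 2.5% |
| 2.4 | Φ(−2.450) = 0.7% | 2.5% |

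Power at SD_t = 2.4, zero true difference, margin 1.5, n = 45: the true SE is 2.4 × 0.2108 = 0.506. With its own variance, power is Φ(1.5/0.506 − 1.96) = 84%. Under CS it is Φ((1.5 − 1.96 × 0.632)/0.506) = 70%.

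**Whole patterns, nine time points, with SD_pool worked out from the pattern.**
- Day 1 at 2.75 and Day 28 at 3.25: SD_pool 3.04. Day 28 coverage is 93.3% and error 3.4%; Day 1 coverage is 97.0% and error 1.5%.
- Day 1 at 2.5 and Day 28 at 3.5: SD_pool 3.10. Day 28 coverage is 91.7% and error 4.2%; Day 1 coverage is 98.5% and error 0.8%.
- One point at 3.6 and eight at 3.0: SD_pool = √((12.96 + 72)/9) = 3.07. Error at that point is 4.7%.
- One point at 4.0 and eight at 3.0: SD_pool 3.13. Error at that point is 6.3%.

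A simulation of 20,000 complete-data trials (four arms of 45, correlation 0.7 within and 0.5 between visits) agrees for equal SDs and for the first two patterns. UN without a random effect gave coverage of 0.947 to 0.952 and error of 0.024 to 0.027 at every point.

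**The all-points rule under CS.** Simulated with 45 per arm, nine points and correlations from 0.5 within and 0.3 between visits up to 0.9 and 0.7. The patterns were one Day 28 point at 3.6 with the rest at 3.0, and all Day 28 points at 3.5 or 3.6 with Day 1 at 2.5 or 2.4. The chance of passing every point was:
- every point at the margin: at most 0.23%;
- all Day 28 points at the margin, no difference on Day 1: at most 1.7%;
- one high-variance point at the margin, no difference elsewhere: about 2.4% to 4.6%.

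The trial-level error cannot exceed the per-point error at a point that lies on the margin, but a steeper spread raises that ceiling. With one point at 3.6 and eight at 2.4, SD_pool = √((12.96 + 46.08)/9) = 2.56 and the ceiling is Φ(−1.96 × 2.56/3.6) = 8.2%.

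**The case against.** The strongest reply is that the SAP may describe a sound model loosely. There are three readings.
- The random subject effect only means that subject is the blocking unit in a repeated-measures model. Nothing is then redundant.
- UN describes a single random intercept. The matrix is 1 × 1 and can be estimated, but the model is already compound symmetry and the fallback changes nothing.
- UN is the residual structure and a random intercept is added. Only here is there a surplus parameter.

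This stands: the text does not settle which is meant. A reader might infer that the primary model cannot be estimated and will drop to CS. The documents do not support that. Under the third reading the total covariance is still determined, and a singular random-effect matrix is not by itself failed convergence. Random intercept plus UN was fitted by a general optimiser to one simulated data set (180 subjects, five time points). It converged from three starting values to the same likelihood and recovered the total covariance to within about 0.0001. That was not the SAS procedure the trial would use, so numerical trouble there cannot be ruled out.

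Two further objections also stand. The harm needs both that CS is in force and that variances differ materially, and the documents are silent on variances. If the main-effects model is used, there is one treatment difference and the per-point mechanism does not apply as described.

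What the reply does not answer is that the second reading gives equal variances from the start, that the only stated fallback does the same, and that the wording leaves the choice to the programmer.

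**Conclusion.** The point holds as a weakness in specification with a conditional consequence. SAP 4.11.1 does not identify the model behind the decisive confidence limits, and its only fallback assumes equal variances under a rule that reads each time point separately.

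On assumed SDs around a pooled value of 3.0, per-point one-sided error at SD 3.6 is 5.1% against 2.5%, and per-point power at SD 2.4 is 70% against 84%. These figures require that CS is in force and that the interaction model is used, and they take the data as complete. With equal variances and complete data there is no loss.

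A reader might take 5.1% as the trial's false-positive rate. It is not. Rows 1 to 3 require success at every time point, and the trial-level rate rises above 2.5% mainly when the high-variance point is the one at the margin. The lost power at low-variance points counts as well, since one failure stops the sequence.

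One effect was not quantified. The +12 hour reading is optional for new subjects under Protocol V3.0 and missing values are not imputed, so a wrong correlation structure could also shift the estimates at that time point.

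**What to change.** Amend SAP 4.11.1 before database lock, as SAP section 1 allows:
- Remove the separate random subject effect. Fit residual TYPE=UN over visit-by-time with subject as the repeated unit, and Kenward-Roger degrees of freedom.
- Define failed convergence, including how a non-positive-definite matrix is treated.
- Replace the CS fallback with a fixed order: heterogeneous Toeplitz, then heterogeneous CS. Use empirical standard errors with a degrees-of-freedom method compatible with them, which Kenward-Roger is not.
- As the last step, use ANCOVA at each time point. SAP 4.11.1 already uses ANCOVA for the group means, and SAP 4.11.2 uses it for treatment differences in the secondary analyses.

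The essential parts are the clear model statement and a separate variance per time point. The particular order of structures and the degrees-of-freedom method are good practice rather than corrections of an error. Protocol 8.4 also names the random subject effect; listing the change in SAP section 5 would cover that. The cost is slightly more SAP text and a few lines of code. No data collection changes.

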4.11.2 Secondary Efficacy Analyses

The secondary efficacy endpoints are all related to IOP in the study eye.

Change from Baseline in IOP at Day 7 and Day 14 in the study eye will be summarised by visit, timepoint and treatment group. The endpoints will be analyzed using an ANCOVA model including baseline value and treatment groups as independent variables. The LS means, SE and 2-sided 95% CI will be reported for each treatment group at each post-randomization visit.

In addition, the differences between treatments (H-1337 vs Timolol) will be calculated and summarised by visit, timepoint and treatment group (for each of the H-1337 groups). The ANCOVA model will be used to calculate the LS mean, SE, and, 2-sided 95% CI for the between-treatments differences.

Similar analyses will be performed for the following endpoints:

- IOP.
- percentage change from Baseline in IOP,
- mean diurnal IOP (12-hour diurnal),
- change from Baseline in mean diurnal IOP (12-hour diurnal),
- percentage change from Baseline in mean diurnal IOP (12-hour diurnal),
- mean diurnal IOP (8-hour diurnal),
- change from Baseline in mean diurnal IOP (8-hour diurnal),
- percentage change from Baseline in mean diurnal IOP (8-hour diurnal).

Where multiple IOP assessments are made on the same day, mean diurnal IOP (12-hour diurnal) is defined as the average of all multiple assessments (Pre T_0 is excluded from the calculation). Mean diurnal IOP (8-hour diurnal) is defined as the average of all assessments up to 04:00pm (Pre T_0 is excluded from the calculation). The visit at which a subject is missing more than (>) 2 assessments for the calculation of mean diurnal IOP will be excluded from the analysis in the PP population.

The number and percentage of subjects with IOP ≤18 mmHg will be summarized by visit, timepoint and treatment group. The 2-sided 95% CI will be calculated using the Clopper-Pearson method. In addition, the difference in proportions between treatments (H-1337 vs Timolol) will be calculated and summarised by visit, timepoint and treatment group (for each of the H-1337 groups). The 2-sided 95% CI for the difference in proportions will be computed using the Wald method.

A similar analysis will be performed for the following 2 endpoints:

- number and percentage of subjects with mean diurnal IOP (12-hour diurnal) ≤18 mmHg, and
- number and percentage of subjects with mean diurnal IOP (8-hour diurnal) ≤18 mmHg.

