1.4 Dose Rationale

Ocular PK data in rabbits and monkeys confirmed that H-1337 exhibits dose-related effects and can reduce IOP for upwards of 8-12 hours. The clinical doses, treatment period (28 days), and dosing regimen (BID) are expected to have an acceptable safety profile and have been selected based on preclinical toxicology data. The total daily administered dose of H-1337 in human subjects will be approximately 1.72 mg/day (or 0.03 mg/kg/day based on a 60-kg individual) when administered twice daily in both eyes at the maximal concentration of 1.0%. In a previous clinical study, 3 concentrations of H-1337 Ophthalmic Solution (0.06%, 0.02% and 0.6%) dosed twice-daily (b.i.d.) provided similar ocular hypotensive outcomes. In the present study, a high concentration of 1.0% is planned to be used both once (q.d.) and twice (b.i.d.)-daily. The dose is supported by preclinical safety studies. The highest dose from the previous study (0.6%, b.i.d.), as well as a positive marketed control, timolol ophthalmic solution 0.5%, b.i.d., will be included for comparison.

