2. STUDY OBJECTIVES

Primary Objective:

• Evaluate the ocular hypotensive efficacy of 3 dose regimens of H-1337 compared to timolol maleate 0.5% in subjects with POAG or OHT treated for up to 28 days.

Secondary Objectives:

• Evaluate the local ocular and systemic safety of 3 dose regimens of H-1337.

Exploratory Objectives:

• Evaluate the efficacy of diurnal IOP measurements of 3 dose regimens of H-1337 compared to timolol 0.5%.

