3. STUDY DESIGN

3.1 Study Design

The trial will evaluate the safety and efficacy of 3 dose regimens of H-1337 (0.6% b.i.d., 1.0% b.i.d. and 1.0% q.a.m., and timolol maleate (0.5%, b.i.d.) OU for 28 days (\pm 2-day allowable window for Day 28).

Approximately 200 subjects will be randomized and dosed for 28 days. The parallel group, double-masked, active-controlled study will include the following dosing cohorts:

- H-1337 0.6% Ophthalmic Solution b.i.d. (n=50)
- H-1337 1.0% Ophthalmic Solution b.i.d. (n=50)
- H-1337 1.0% Ophthalmic Solution q.a.m. and H-1337 placebo q.p.m. (n=50)
- Timolol 0.5% Ophthalmic Solution b.i.d (n=50)

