4.5 Monitoring for Subject Compliance

Subjects or their caretakers will administer study medications according to the IP dosing instructions and training provided, ie; as close as possible to 8 a.m. and 8 p.m. Compliance will be assessed at each visit by asking the subject for their recollection about any missed doses. Confirmation of compliant IP dosing the evening prior to a study visit must be confirmed or the visit should be rescheduled. If the subject reports missing more than 4 doses since the prior visit, a Protocol Deviation will be documented and the subject will be counseled on IP compliance.

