4.1 Definitions and Conventions

Listings present the subjects individual data, while summary tables present the summary statistics of subjects data.

Summary statistics will be presented for continuous variables, by way of n, mean, standard deviation (SD), median, minimum and maximum. For categorical variables including binary variables, frequency counts and percentages will be presented. Percentages will be calculated using the total number of subjects per treatment groups or the total number of subjects with an assessment per treatment groups, depending on the nature of the analysis.

In addition, 95% 2-sided confidence intervals (CIs) will be presented, where relevant. In case of percentages, the CI will be computed using the Clopper-Pearson method. The CI will be computed for continuous variables using a t-test analysis.

Summary statistics will be displayed by treatment groups, which will be labelled as follow:

- Group 1: H-1337 0.6%
- Group 2: H-1337 1.0% b.i.d
- Group 3: H-1337 1.0% q.a.m
- Group 4: Timolol 0.5%

Baseline Value is defined as the last non-missing value prior to the first IP administration for vital signs, BCVA, biomicroscopy and dilated ophthalmoscopy (Day 1 Pre- T_0 for vital signs, BCVA and biomicroscopy; Screening for dilated ophthalmoscopy). For IOP and conjunctival hyperemia grading, time-matched baseline values are defined at Pre- T_0 on Day 1 (Visit 3), T_0 +2 hours, T_0 +4 hours, T_0 +8 hours and T_0 +12 hours on Day 0 (Visit 2). For mean diurnal IOP, baseline is defined at Day 0.

Change from Baseline is defined as the difference in value of the assessment between the considered visit and the baseline value. In the case of IOP and conjunctival hyperemia grading, change from Baseline is the difference in value of the assessment between the considered visit at a particular timepoint and the corresponding baseline value.

Study eye is defined as the eye that meets all entry criteria including the IOP criteria after washout. Should both eyes meet the criteria then the study eye will be the eye with the higher 8 am IOP at Baseline (Day 1). If both eyes have the same 8 am IOP at Baseline (Day 1), the study eye will be the right eye.

SAS® version 9.4 or above will be used to perform the analyses.

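### Both mean diurnal IOP measures omit the Day 28 pre-dose reading, the q.a.m. arm's only end-of-interval value, and the 8-hour mean's 4 pm cut-off conflicts with time points counted from dosing

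*SAP*

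**What the plan says.** SAP 4.11.2 defines two averages for days with several IOP readings. For the first, "mean diurnal IOP (12-hour diurnal) is defined as the average of all multiple assessments (Pre T_0 is excluded from the calculation". For the second, "Mean diurnal IOP (8-hour diurnal) is defined as the average of all assessments up to 04:00pm (Pre T_0 is excluded from the calculation". Neither exclusion is limited to a visit, so both cover Day 0, Day 1 and Day 28. SAP 4.1 adds: "For mean diurnal IOP, baseline is defined at Day 0". The value, change, percentage change and the proportion at or below 18 mmHg are all derived from these means.

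Protocol 6.1 lists mean diurnal IOP as a secondary endpoint without saying which readings enter it. The SAP supplies that rule, gives no reason for it, and does not list it among its changes from the protocol (SAP 5).

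Dosing is "as close as possible to 8 a.m. and 8 p.m" (Protocol 4.5). On visit days the morning dose follows the morning IOP and the evening dose follows the evening IOP (Protocol 5). One arm is "H-1337 1.0% Ophthalmic Solution q.a.m. and H-1337 placebo q.p.m. (n=50" (Protocol 3.1). The only duration of effect given is from rabbits and monkeys: H-1337 "can reduce IOP for upwards of 8-12 hours" (Protocol 1.4).

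Footnotes to the schedule define T0 as the actual morning dosing time, expected at 8 am ± 30 minutes, count the later time points from T0, and make T0+12 optional for new subjects under protocol version 3.0.

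**The concern.** Pre-T0 means different things on different days. On Day 1 no study drug has been given, and leaving the reading out of an on-treatment average is proper. On Day 28 it is an on-treatment reading at the end of a dosing interval. In the q.a.m. arm the evening bottle is placebo, so no other reading that day is an end-of-interval value for that regimen.

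The omission does not fall equally on the arms in the 12-hour mean. T0+12 is read before the evening drop, so it is an end-of-interval value for b.i.d. and timolol, and it counts where it was taken. The q.a.m. equivalent never counts. In the 8-hour mean no arm has an end-of-interval reading.

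If the q.a.m. effect wanes before the next drop, these means and their responder rates will favour q.a.m. A reader comparing regimens on a measure called diurnal control could take it to cover the whole dosing interval.

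The 4 pm limit is a separate problem. It is a clock time applied to readings scheduled from T0, so which readings are averaged can depend on minutes of dosing time and can differ between Day 0 and Day 28 in one subject.

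**Working it through.** **Inputs.** Definitions: SAP 4.11.2 and 4.1. Dosing order: Protocol 5. Time points and spacing: schedule footnotes. SD 3.0 mmHg and 45 evaluable per group: SAP 3.3. The correlation between readings is not in the documents; I assume 0.5 to 0.9.

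**The plan's own figure.** None is given for the diurnal endpoints. The sizing whose SD and n are reused below does reproduce: for a 2 mmHg limit, SD 3.0, one-sided 0.05 and true difference 0, the standard error at 45 per group is 3·√(2/45) = 0.632, and power is Φ(2/0.632 − 1.645) = 93.5% (93.2% with the t distribution). The SAP says at least 90%. Also 45/0.9 = 50.

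**What each Day 28 reading represents.**

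| Reading | Hours since active drop: b.i.d., timolol | Hours since active drop: q.a.m. | In 12-hour mean | In 8-hour mean |
|---|---|---|---|---|
| Pre-T0 | about 12 (end of interval) | about 24 (end of interval) | no | no |
| T0+2 | 2 | 2 | yes | yes |
| T0+4 | 4 | 4 | yes | yes |
| T0+8 | 8 | 8 | yes | yes, if by 4 pm |
| T0+12, where taken | 12 (end of interval) | 12 (mid-interval) | yes | no |

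Where T0+12 is skipped, the 12-hour mean reduces to the +2, +4 and +8 h readings.

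**Effect on the mean.** Suppose q.a.m. is L mmHg worse than timolol at Day 28 Pre-T0 and equal elsewhere. As written, both means move by 0. With Pre-T0 included:

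- 8-hour mean, four readings: L/4. L = 2 gives 0.50; L = 3 gives 0.75; L = 4 gives 1.00.
- 12-hour mean, five readings: L/5. L = 2 gives 0.40; L = 3 gives 0.60; L = 4 gives 0.80.

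**How well an inclusive mean would detect a trough loss.** The SD of a mean of k readings is 3·√((1 + (k−1)ρ)/k). For ρ = 0.5 to 0.9 this is 2.37 to 2.89 (k = 4) or 2.32 to 2.88 (k = 5). At 45 per group and two-sided 0.05, power to see L = 2 is 13–17% for the 8-hour mean and 10–13% for the 12-hour mean. The Pre-T0 time point alone gives Φ(2/0.632 − 1.96) = 88.5%.

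**Responder rate, invented readings.** Day 28 values of 23 (Pre-T0), 17, 18 and 18 give (17+18+18)/3 = 17.7, a responder at 18 mmHg. With Pre-T0, (23+17+18+18)/4 = 19.0, a non-responder.

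**Clock limit.** T0 between 7:30 and 8:30 puts an on-time +8 h reading between 15:30 and 16:30. With T0 at 8:10 it falls at 16:10; read literally, the rule drops it and leaves a two-reading mean. Not every such subject is affected: the footnote sets minimum gaps of 1.5, 1.5 and 3.5 h, so the earliest permitted +8 h reading is 6.5 h after T0, or 14:40 in this example.

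**The case against.** The strongest reply is that the trough is examined in a better place. Day 28 Pre-T0 is one of the primary non-inferiority time points (five on that day in the SAP, four in the protocol), and the q.a.m. row requires the 1.5 mmHg threshold at every listed point, so failure there alone fails the regimen. Days 7 and 14 have only a Pre-T0 reading, so their comparisons are trough comparisons. The proportion at or below 18 mmHg is also reported by time point. The diurnal means lie outside the testing hierarchy, a post-dose daytime average is a legitimate summary, and the present definition matches across Days 0, 1 and 28.

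Most of this stands. A reader might infer that the trial cannot show whether a regimen holds IOP until the next dose. The documents do not support that, for the reasons just given; nor does the omission affect all regimens alike, since the 12-hour mean keeps a b.i.d. and timolol end-of-interval reading. A reader might also infer that restoring Pre-T0 would make the mean a sound test of duration. It would not, because the loss is diluted to a quarter or a fifth. Nor should a shift in the mean be judged against the 1.5 mmHg margin, which is set per time point.

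Two limits on the reply remain. The q.a.m. comparison is third in a fixed sequence, so its formal test may not be reached, though the estimates are still reported. And SAP 4.11.1 falls back to a main-effect model if no interaction is detected, which could pool time points and needs reconciling with the point-by-point rule in SAP 4.3. Neither limit touches the Day 7 and Day 14 comparisons.

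On the clock limit, 4 pm was probably meant as nominal 8 am plus 8 hours. The text does not say so.

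**Conclusion.** The point holds, at modest size. As written, neither diurnal mean carries any q.a.m. end-of-interval information on Day 28, while the 12-hour mean carries it for b.i.d. and timolol where T0+12 was taken. The means and their responder rates should not be read as evidence of control through the dosing interval. That evidence comes from Pre-T0 at Days 7, 14 and 28, already planned. The tilt toward q.a.m. rests on its effect waning before the next drop. The animal data make that plausible, but no document gives a human trough difference, so L above is illustrative.

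The 4 pm limit is a definite inconsistency with time points counted from T0. It affects on-time +8 h readings when T0 is after 8:00, not every subject dosed after 8:00.

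No primary conclusion depends on either issue.

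**What to change.** In SAP 4.11.2, before database lock:

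1. Define the 8-hour mean by nominal time points through T0+8 h in place of the clock limit.
2. Keep the post-dose means, so that Day 1 and Day 28 stay comparable. Add a pre-specified Day 28 mean that includes Pre-T0, in 8-hour and 12-hour versions, with responder rates. Its baseline should be the Day 0 mean of the same nominal time points, including Day 0 Pre-T0. State this explicitly, because the SAP's single-time-point baseline for Pre-T0 is the Day 1 value.
3. State that duration of effect is judged from the Pre-T0 time-point results, not from the diurnal means.

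All the readings are already scheduled, so the cost is SAP wording and programming. The downsides are extra derived variables with their own baseline, and a q.a.m. diurnal figure that may look less favourable.
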